2.6 Sample size estimation

The sample size was calculated using PASS 16 Power Analysis and Sample Size Software (2018), NCSS, LLC., Kaysville, Utah, USA (ncss.com/software/pass). The sample size was calculated with 90% power and a 2.5% 1-sided type 1 error rate based on the following assumptions:

- 1:1 randomization allocation
- Percent of rTNSS responders in active treatment group = 73.5% (95% CI, 63.6% to 81.9%)
- Percent of rTNSS responders in sham control group = 45%

The active response rate is based on the 90-day response rate in FROST. ¹² The sham control group rate is based on the placebo rate reported by Benninger et al for a systematic review of rhinitis pharmaceutical studies. ¹³ In the drug trials evaluated, they reported mean placebo reponse rates of -15.0% (range -7.6% to -40.0%) at 2-week follow-up for seasonal allergic rhinitis and -24.8% (range -14.4% to -37.2%) at 4- to 6-week follow-up for perennial allergic rhinitis. To ensure adequate sample size, the anticipated placebo rate was slightly overestimated from these values.

Additionally, powering the sample size for subgroup analysis of allergic vs nonallergic participant rTNSS responses was considered. However, data from the FROST study (**Table 1**)¹² indicated that there is no difference in response rates between allergic and nonallergic patients and that the groups are poolable at the 90-day follow-up period, so enrollment by allergy subgroup was not incorporated into the sample size calculation. An assessment of poolability by allergy subgroup will be performed during analysis.

Table 1. FROST 90-Day Total rTNSS Responder Rate by Allergy Subgroups

Group	Improved ≥30%
Allergic	73.3% (22/30)
Nonallergic	73.5% (50/68)

Under the assumptions outlined above, a total sample size of 122 randomized participants (61 per arm) is adequate to test this hypothesis. To account for approximately 5% attrition at 90 days, a total of 128 participants will be enrolled in the study.

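### FROST does not establish that allergic and nonallergic patients can be pooled, and the undefined poolability check would give only weak evidence of an equal effect

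*Combined protocol and SAP*

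**What the plan says.** Section 2.6 of the combined protocol and SAP says that sizing the trial for an allergic versus nonallergic analysis was considered. It was set aside because the FROST data "indicated that there is no difference in response rates between allergic and nonallergic patients and that the groups are poolable" at 90 days. Table 1 in that section gives the evidence: 22/30 (73.3%) allergic and 50/68 (73.5%) nonallergic responders. The table has no sham column.

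The same section then promises a check: "An assessment of poolability by allergy subgroup will be performed during analysis". Neither Section 2.6 nor Section 2.7 names its test, effect scale, significance level, margin or consequence.

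Section 2.10.4 stratifies randomization by allergy subgroup and sets no quota for either one. Sections 2.5 and 2.7 describe the primary comparison as an unstratified test of two proportions, one-sided at 0.025.

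**The concern.** Two nearly equal percentages from 30 and 68 patients do not show equality; the interval around their difference has to be read. The quantity is also not the one at issue. This trial pools the active-minus-sham difference, and equal response on treatment implies equal effect only if sham response is equal too, which Table 1 cannot show.

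The planned check does not clearly repair this. If it is a conventional interaction test in about 122 people, a non-significant result is likely even when the effect differs greatly between subgroups. At stake is how far a positive pooled result carries. The objective covers chronic rhinitis as a whole, so a result driven by one subgroup could be reported for both, supported by a check with little ability to tell them apart.

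**Working it through.** **Reproducing the plan's own figures.** Section 2.6 states: "The sample size was calculated with 90% power and a 2.5% 1-sided type 1 error rate". With 73.5% active, 45% sham and 1:1 allocation, the mean rate is 0.5925, and the pooled-variance formula gives

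n = [1.960·√(2·0.5925·0.4075) + 1.282·√(0.735·0.265 + 0.45·0.55)]² / 0.285² = 60.4, so 61 per arm.

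This matches "a total sample size of 122 randomized participants (61 per arm) is adequate to test this hypothesis". The exact CI for the combined FROST rate, (22+50)/(30+68) = 72/98, is 63.6% to 81.9%, also as stated.

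**The FROST difference.** 22/30 - 50/68 = 0.7333 - 0.7353 = -0.2 points.

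- Wald: SE = √(0.7333·0.2667/30 + 0.7353·0.2647/68) = 0.0969, so the 95% CI is -19.2 to +18.8 points.
- Newcombe: the Wilson limits are 55.6% to 85.8% and 62.0% to 82.6%. Lower limit: -0.2 - √(17.8² + 9.0²) = -20.1. Upper limit: -0.2 + √(12.5² + 11.5²) = +16.8.

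A gap of 19 points is two-thirds of the planned effect (19/28.5).

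**What an interaction test could detect.** The documents give neither the allergic share nor the test, so these are assumptions: the FROST share of 30/98 = 31%; 61 evaluable per arm, hence 61·30/98 = 18.7 allergic and 42.3 nonallergic per arm; 45% versus 45% in allergic and 73.5% versus 45% in nonallergic participants; a two-sided Wald test on the risk difference.

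- Allergic variance: (0.2475 + 0.2475)/18.7 = 0.0265
- Nonallergic variance: (0.1948 + 0.2475)/42.3 = 0.0105
- SE of the interaction: √0.0370 = 0.192; standardised effect: 0.285/0.192 = 1.48
- Power: Φ(1.48 - z) plus a negligible opposite tail, with z = 1.960, 1.645 and 1.440

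| Two-sided level | Power | Missed |
|---|---|---|
| 0.05 | 32% | 68% |
| 0.10 | 44% | 56% |
| 0.15 | 52% | 48% |

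Sensitivity to the allergic share (risk-difference scale): at 20% allergic, power is 25%, 36% and 44%; at 50%, it is 37%, 49% and 57%. If the allergic effect is half the planned one (14.25 points, 31% share), power is 12% at 0.05 and 26% at 0.15.

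**Could the pooled test still succeed?** In the 31% zero-effect case the overall active rate is 0.306·45% + 0.694·73.5% = 64.8%. Against 45% with 61 per arm, the pooled primary test has about 59% power.

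**Precision by subgroup at 31% allergic.** The 95% half-width for active minus sham is 1.96·√0.0265 = 32 points in allergic participants (30 if their active rate is 73.5%), and 1.96·√0.0105 = 20 points in nonallergic participants.

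**The case against.** A reader might infer that the check would usually miss a device that does nothing in allergic patients. The documents do not support that as a general statement, because they fix no test or level. At 0.15 and a 31% share, detection is slightly more likely than not. Detection also improves with a larger contrast: if the overall active rate stays at 73.5%, the nonallergic active rate must be about 86%, and power at 0.05 rises to 59-66% depending on the scale.

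The 45% versus 45% scenario also sits badly with Table 1. If the allergic response on ClariFix were truly 45%, 22 or more responders out of 30 would have probability about 0.002. A zero effect consistent with Table 1 needs an allergic sham rate near 73%, far above the planned 45%. Power is then 36% at 0.05 and 57% at 0.15, so the check remains weak at 0.05 but does not usually fail at 0.15.

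A reader might also infer that the primary test depends on the check. Sections 2.3.1, 2.5 and 2.7 describe a single comparison of the arms with no such condition, so an explicit sentence would only confirm what is there. Nor does any section say that a non-significant check will be used to claim benefit in each subgroup.

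Finally, not powering for an interaction is an ordinary choice: 80% power at 0.05 would need roughly 365 to 440 participants. Table 1 comes from an internal report, and Section 2.3.3 refers to a Statistical Analysis Plan for exploratory outcomes; any fuller poolability analysis in either cannot be judged here.

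These arguments limit the claim about miss rates. They do not rescue the equality statement, the absence of a sham comparison, or the undefined check.

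**Conclusion.** The point holds in a limited form. The FROST comparison is compatible with differences of nearly 20 points in either direction and concerns treated response only, so it does not establish that the active-minus-sham effect can be assumed equal. This part needs no assumption about power.

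The poolability assessment is undefined. Under the stated assumptions, a conventional interaction test would miss a zero effect in allergic patients between about half and two-thirds of the time. A non-significant result would therefore be weak evidence of equal effect. These rates depend on the assumed allergic share, level and scenario, and should not be quoted as properties of the plan itself.

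The sample size is not in question: 61 per arm rests on the overall rates and reproduces exactly.

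**What to change.** Three changes, made before any comparison of the arms is run:

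1. In Section 2.6, replace the no-difference statement with the estimate: -0.2 points, 95% CI -20 to +17 (Newcombe), ClariFix-treated patients only, no information on the effect against sham.
2. In Sections 2.5 and 2.7, analyse the pooled primary endpoint stratified by allergy subgroup, for example with a Cochran-Mantel-Haenszel test, since that factor already stratifies randomization. State that this analysis stands whatever the subgroup results show.
3. Replace the poolability sentence with a commitment to report the active-minus-sham responder difference in each allergy subgroup and the difference between subgroups, each with a 95% CI. Describe these as low-powered, give the expected half-widths (about 30-32 points allergic and 20 points nonallergic at FROST's mix), and say that non-significance will not be taken as evidence of equal effect.

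The cost is a small change to the primary test method, a few table rows, and a less favourable account of the evidence for pooling. No patients or visits are added, and 122 evaluable and 128 enrolled are unaffected.

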2.7 Data analyses

Summary statistics will be calculated for all study endpoints. Categorical variables will be summarized using frequency distributions and continuous variables will be summarized with means and standard deviations (normal distributions) or medians and ranges (non-normal distributions). Confidence intervals (95% CI) may be computed for select study endpoint measures. The primary efficacy endpoint will be tested at a 1-sided alpha level of 0.025 using a Chi-square test. The secondary endpoints will be tested at a 2-sided alpha level of 0.05.

Participants who are randomized but drop out before receiving their randomized treatment (active treatment or sham procedure) will not be considered enrolled in the study. Participants who are unblinded before the 90-day visit due to medical necessity will not be included in the analysis of efficacy endpoints. For long-term follow-up analyses, crossover participants will be analyzed with the active treatment participants.

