2.5 Study hypothesis

The primary endpoint is the percentage of participants in each arm who achieve an improvement ≥30% in total rTNSS score at 90 days compared with baseline. The primary endpoint will be compared between treatment groups for superiority of active to sham treatment by testing the following 1-sided hypotheses using the Z-test of 2 proportions:

 H_0 : $p_{ClariFix} \le p_{sham}$

versus

 H_A : $p_{ClariFix} > p_{sham}$

where $p_{ClariFix}$ and p_{sham} are the percentages of responders in the active ClariFix and sham groups, respectively.

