2.10.4 Randomization and blinding

Randomization assignments will be generated by in independent statistician using variable block size distribution by site with a 1:1 allocation to active or sham treatment. Randomization will also be stratified by allergy subgroup (allergic, nonallergic). The randomization schedule will be entered into the Medrio electronic data collection (EDC) randomization module. Randomization will occur on the day of the procedure and after all baseline data have been collected and eligibility has been confirmed. All randomized and treated participants will be considered enrolled. Confirmation of randomization assignment from EDC will be printed and filed in the study record.

This is a single-blind study; participants will be blinded to the randomized assignment. To facilitate blinding, control participants will undergo a sham procedure using the ClariFix device without a cryogen cannister. To support blinding, participants will wear blindfolds during the procedure to limit any visual clues that may suggest the treatment assignment. A separate device with a canister held near the participant will be used to provide the sound of the gas release from the cannister. A standardized script for the physician/staff will be used during the procedure to assure blinding. Additionally, local anesthesia regimes will be the same for both treatment groups within each investigational center.

Participants will complete a blinding questionnaire at completion of the procedure and at the 30-day and 90-day follow-up visits to assess the adequacy of the blinding procedures. Upon

completion of their 90-day visit, each participant will be unblinded. Sham control participants will be offered the opportunity to receive active treatment if they wish and still meet eligibility criteria.

Before the 90-day visit, unblinding of participants will only occur when medically necessary. In the event of a device-or procedure-related SAE, the sponsor may authorize the site to unblind the participant in order to adequately assess the event.

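### The primary responder test leaves out the randomization factors (site and allergy subgroup): it is valid and keeps its planned 90% power, but it is conservative if sites differ and is cheap to improve

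*Combined protocol and SAP*

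**What the plan says.** **Randomization.** Section 2.10.4 of the protocol generates assignments "using variable block size distribution by site with a 1:1 allocation to active or sham treatment", and adds: "Randomization will also be stratified by allergy subgroup (allergic, nonallergic". Section 2.4 allows up to 12 centers, so there can be up to 24 site-by-allergy strata.

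**Primary test.** Section 2.5 compares the arms "by testing the following 1-sided hypotheses using the Z-test of 2 proportions". Section 2.7 says: "The primary efficacy endpoint will be tested at a 1-sided alpha level of 0.025 using a Chi-square test". Neither section names site or allergy subgroup. Without a continuity correction the pooled Z statistic squared is the chi-square statistic, so the two descriptions are treated here as one unstratified test.

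**Other provisions.** Section 2.6 plans a poolability assessment by allergy subgroup but does not say what follows for the primary test if pooling is not supported. No analysis provision mentions site. On intervals, section 2.7 says only: "Confidence intervals (95% CI) may be computed for select study endpoint measures". No interval or interval method is fixed for the primary endpoint.

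**The concern.** Blocking within site and allergy subgroup balances the arms on both factors. The between-stratum part of the outcome variation then largely cancels from the treatment difference, but an unstratified variance still counts it as noise. If strata differ in response, the standard error is too large, the test runs below its nominal level, and some of the precision bought by stratifying is not used.

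The protocol itself leaves room for site differences. Local anesthesia follows each physician's practice and is matched between arms only within a center, a second application on each side is left to the physician (sections 2.10.4 and 2.10.5), and the outcome is self-reported (section 2.11.1). How large such differences are, the documents do not say.

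There is also a gap that needs no assumption about sites: the plan does not commit to an effect estimate with an interval for its primary endpoint.

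**Working it through.** **Inputs.** From section 2.6: responder rates 73.5% and 45%, 1:1 allocation, one-sided alpha 0.025, 90% power, 61 per arm, and prior-study rates of 22/30 (allergic) and 50/68 (nonallergic). From section 2.4: up to 12 sites. Assumed, because the documents are silent: the between-site spread, equal expected site sizes, and blocks of 2 or 4.

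**1. The plan's own figure.** With mean rate 0.5925, the pooled formula without continuity correction is

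n = [1.960 × √(2 × 0.5925 × 0.4075) + 1.282 × √(0.735 × 0.265 + 0.45 × 0.55)]² / 0.285² = (1.3620 + 0.8523)² / 0.08123 = 60.4,

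so 61 per arm and 122 in total, as stated. Power at 61 per arm is 90.3%. (With a continuity correction the total would be 136, so the stated size belongs to the uncorrected test.)

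**2. Large-sample effect of ignoring sites.** Let τ be the between-site SD of the response rate, common to both arms.

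- Reported SE under the alternative: √(0.442275/61) = 0.0851. True SE under within-site balance: √((0.442275 − 2τ²)/61).
- Null SE used by the test: √(2 × 0.24144/61) = 0.0890. Null SE respecting sites: √(2 × (0.24144 − τ²)/61).
- Actual one-sided level: 1 − Φ(1.960 × √(0.24144/(0.24144 − τ²))).
- Power: Φ((0.285 − 1.960 × null SE)/true SE), using each null SE in turn.

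| τ (points) | True/reported SE | Level of unstratified test | Power, unstratified | Power, SE respecting sites |
|---|---|---|---|---|
| 5 | 0.994 | 2.44% | 90.4% | 90.6% |
| 10 | 0.977 | 2.26% | 90.8% | 91.5% |
| 15 | 0.948 | 1.98% | 91.5% | 93.0% |
| 20 | 0.905 | 1.59% | 92.4% | 94.9% |

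The gap is 0.7, 1.5 and 2.5 points at τ = 10, 15 and 20. Unstratified power does not fall below plan.

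**3. Allergy.** Here the between-stratum variance is (30/98)(68/98) × gap² = 0.2124 × gap². The SE ratio is 1.000 at the prior-study gap of 0.2 points, 0.995 at 10 points, 0.981 at 20 and 0.956 at 30. The half-width of an unstratified 95% interval would be 16.7 points, against 16.6, 16.4 and 16.0 for the last three gaps.

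**4. Simulated CMH tests.** The large-sample figures ignore the cost of sparse strata. With 122 participants in 24 strata the average is 122/24 = 5.1 per stratum. In simulation about 2.6 participants per trial fell in strata holding only one arm and so contributed nothing. Power with 12 sites, 30/98 allergic, no allergy effect and 7,000 trials per row (Monte Carlo error about 0.4 points):

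| Site SD, logit (sham-rate SD) | Unstratified | CMH by site | CMH by site × allergy |
|---|---|---|---|
| 0 | 91.0% | 90.1% | 89.1% |
| 0.5 (12 points) | 91.2% | 91.2% | 90.3% |
| 0.75 (17 points) | 91.6% | 92.6% | 92.0% |
| 1.0 (21 points) | 91.9% | 93.9% | 93.3% |

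A separate simulation (4,000 trials per setting) at logit SD 0, 0.5, 0.8 and 1.0 agrees: unstratified 90.3, 90.7, 92.1 and 92.3%; by site 89.2, 90.4, 93.5 and 94.2%; by site × allergy 88.5, 89.7, 92.8 and 93.4%.

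With 6 sites instead of 12, site × allergy breaks even at SD 0.5 (91.1% for both tests) and gains at SD 1.0 (93.5% against 91.8%). Fewer, larger strata reduce the cost.

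**5. Type I error.** With a common rate of 60% and 6,000 trials per setting (Monte Carlo error about 0.2 points), the unstratified level was 2.60, 2.28 and 2.02% at site SD 0, 0.5 and 1.0. The site × allergy CMH level was 2.40, 2.47 and 2.62%. The exact level of the uncorrected test at 61 per arm with no strata effect is 2.57 to 2.78% for common rates of 73.5% down to 45%. That small excess comes from discreteness, not from ignoring strata.

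**The case against.** The strongest reply is that no planned property fails. The stated sample size reproduces, unstratified power in the re-derivation's simulations was 90.0 to 92.7%, and any error in level is in the safe direction. This stands. A reader might infer that the trial is underpowered or its type I error compromised; the documents' own figures support neither. Power is given up only relative to a different test.

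Second, stratifying is not a gain whenever strata differ. At a site SD of 0.5 on the logit scale, site × allergy CMH is slightly worse than the planned test, and with no site differences it falls below 90% (89.1% and 88.5% in the two simulations). This also stands, and it is why small sites need pooling.

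Third, the site spread is assumed, and the larger values are wide. This stands too: the size of the benefit is conditional.

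Fourth, the prior-study rates by allergy subgroup, 73.3% and 73.5%, show no gap. This stands in part. They come from active treatment only, and the 95% interval for their difference is about ±19 points (1.96 × √(0.1956/30 + 0.1946/68) = 0.19). They neither show a gap nor rule one out.

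Fifth, one might infer that the reported interval will be too wide. No primary interval is specified, so that would apply only if an unstratified one were reported. Finally, the protocol defers exploratory outcomes to a Statistical Analysis Plan, and no separate text of it is in the supplied document, so a stratified analysis there cannot be excluded.

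**Conclusion.** The mismatch is real: randomization uses site and allergy subgroup, and the primary test uses neither. Its consequence is limited to efficiency and calibration. The planned 90% power and N = 122 hold, and the mismatch does not inflate type I error.

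If sites differ with an SD of 10 to 20 points, the one-sided level falls to about 2.3% to 1.6%, and about 1 to 2.5 points of power are forgone against an ideal analysis. CMH with 12 sites recovers part of this: 1.0 (by site) or 0.4 (site × allergy) points at a 17-point SD, and 2.0 or 1.4 points at a 21-point SD. Break-even is near a logit SD of 0.5 for site alone and between 0.5 and 0.75 for site × allergy.

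The mismatch and its direction are certain; the size rests on an assumed site spread, equal expected site sizes and blocks of 2 or 4. This is a cheap improvement with a modest gain, not a defect that threatens the primary conclusion.

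**What to change.** In sections 2.5 and 2.7:

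- Name one primary test: CMH, one-sided at 0.025, stratified by allergy subgroup and site.
- State a rule for pooling small sites so that strata are not sparse, and fix it before any by-arm data are seen.
- Commit to reporting the Mantel-Haenszel difference in responder proportions with its two-sided 95% CI.
- Keep the unstratified chi-square test as a sensitivity analysis.

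**Cost.** The change is to wording only: site and allergy subgroup are already recorded for randomization, and the sample size does not change. If sites do not differ, power falls by about 1 point with stratification by site, or about 2 points with unpooled site × allergy strata. Pooling is meant to limit the latter.

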2.3 Study endpoints

2.3.1 Primary endpoint

The primary endpoint is the percentage of responders at 90 days. Responders are defined as participants with a 30% or greater reduction in rTNSS relative to baseline. The active treatment group will be compared with the sham-control group.

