2.8.1 Inclusion criteria

Study participants MUST meet all of the following criteria:

- 1. Be \geq 21 years of age.
- 2. Has been diagnosed with chronic nonallergic or allergic rhinitis.
- 3. Have moderate to severe symptoms of rhinorrhea (individual rTNSS symptom rating of 2 or 3), mild to severe symptoms of nasal congestion (individual rTNSS symptom rating of 1, 2, or 3), and a minimum total rTNSS score of 4 (out of 12) at baseline.
- 4. Have an allergy test (by skin prick or intradermal testing or by validated *in vitro* tests for specific Immunoglobin E [IgE]) on file within 12 months of the baseline visit.
- 5. Be an appropriate candidate for bilateral ClariFix treatment performed under local anesthesia.
- 6. Be willing and able to comply with all study elements, as indicated by their written informed consent.

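### The primary responder test is valid and meets its stated power but leaves baseline rTNSS unused; pre-specified baseline adjustment may add modest precision and would deal with chance imbalance

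*Combined protocol and SAP*

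**What the plan says.** Section 2.7 (Data analyses): "The primary efficacy endpoint will be tested at a 1-sided alpha level of 0.025 using a Chi-square test". Section 2.5 (Study hypothesis) tests "1-sided hypotheses using the Z-test of 2 proportions". The squared pooled Z statistic is the uncorrected Chi-square statistic, so both names describe one crude comparison. Neither section names a covariate or an adjusted sensitivity analysis.

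Section 2.3.1 sets the endpoint: "Responders are defined as participants with a 30% or greater reduction in rTNSS relative to baseline". Section 2.11.1 builds the score from four items rated 0 to 3, giving a total of 0 to 12. Section 2.8.1 requires "a minimum total rTNSS score of 4 (out of 12) at baseline".

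Baseline rTNSS is recorded at the baseline visit (2.10.3). Section 2.10.4 places randomization after baseline data collection, blocked by site and stratified by allergy subgroup. Baseline rTNSS is not a stratum. The supplied text leaves only exploratory outcomes to the Statistical Analysis Plan (2.3.3) and contains no further model for the primary endpoint.

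**The concern.** The baseline score is part of the endpoint, and there are two reasons to expect the chance of response to depend on it in both arms. A percentage rule on a whole-number scale sets a hurdle that changes with the starting score. Visit-to-visit variation also makes high scores more likely to fall and low scores more likely to rise.

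If response does depend on baseline, a test that ignores it may leave some explainable variation in the risk difference. Any chance difference in mean baseline between arms then passes into the observed result. If the arms differ visibly at readout, the plan offers no pre-specified way to answer the question, and an adjustment chosen afterwards carries less weight.

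**Working it through.** **Inputs from the documents.** Responder rates 73.5% and 45%, 1:1 allocation, 1-sided alpha 0.025, 90% power, 61 per arm (2.6); score range 0 to 12 (2.11.1); entry at 4 or more (2.8.1). **Assumed:** the baseline distribution and the relation between baseline and follow-up scores. The documents give neither.

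**1. The plan's own figure.** With pooled variance under the null and mean rate 0.5925:

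n = [1.960 × √(2 × 0.5925 × 0.4075) + 1.282 × √(0.735 × 0.265 + 0.45 × 0.55)]² / 0.285² = (1.362 + 0.852)² / 0.0812 = 60.4, so 61 per arm.

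This agrees with 2.6. Power at 61 per arm is 90.3% by this formula and 90.7% by exact binomial calculation.

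**2. The hurdle.** Smallest whole-point drop = 0.30 × baseline, rounded up.

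| Baseline | 4 | 5 | 6 | 7 | 8 | 9 | 10 | 11 | 12 |
|---|---|---|---|---|---|---|---|---|---|
| Points needed | 2 | 2 | 2 | 3 | 3 | 3 | 3 | 4 | 4 |
| As % of baseline | 50 | 40 | 33 | 43 | 38 | 33 | 30 | 36 | 33 |

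This is a sawtooth, not a steady trend.

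**3. Effect on precision.** Simulation, 4,000 trials per scenario at 61 per arm, calibrated to 45% and 73.5%. Two baseline distributions were assumed: mean 6.24, SD 1.82 (the pilot mean in 1.2 was 6.2) and mean 7.48, SD 1.92. The follow-up mean was linear in baseline with slope 1.0 (no regression to the mean) down to 0.3 (strong), or proportional to baseline. The adjusted analysis was a linear risk-difference model with arm, baseline and their interaction, with a robust standard error. Each cell gives the lower-mean, then the higher-mean distribution.

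| Relation | Sham response at baseline 4 → 10 | Variance ratio, adjusted/crude | Power, crude → adjusted |
|---|---|---|---|
| Slope 1.0 | 51→36%; 57→41% | 0.986; 0.982 | 90.8→91.0; 91.1→91.0 |
| Slope 0.7 | 41→54%; 40→53% | 1.006; 1.010 | 89.9→89.7; 90.2→89.8 |
| Slope 0.5 | 33→68%; 28→63% | 0.983; 0.974 | 90.6→90.6; 90.0→90.6 |
| Slope 0.3 | 26→79%; 18→71% | 0.935; 0.942 | 90.4→92.1; 91.6→93.0 |
| Proportional | 38→52%; 37→51% | 1.014; 1.011 | 90.1→90.0; 90.6→90.4 |

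The two mechanisms pull in opposite directions. With no regression to the mean, the hurdle makes response fall with baseline. Regression to the mean makes it rise. In between they largely cancel, and 4 of the 10 scenarios show no gain.

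Two other models give the same picture:
- A latent score plus visit noise (between-person SD 1.5, within-person SD 1.0 to 2.0), analysed by logistic g-computation: variance ratios 0.98, 0.95, 0.96 and 0.93, with power gains of 0.5, 1.4, 0.7 and 2.4 points. At within-person SD 0.5 there was neither gain nor meaningful loss.
- A model applying the item-level entry rules of 2.8.1: ratios 0.93 to 1.01, with power changes of about -0.3 to +2.0 points.

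A ratio of 0.94 is worth 122 × 0.06 ≈ 7 participants.

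**4. Chance imbalance.** The SD of the difference in mean baseline is SD × √(2/61): 1.82 × 0.181 = 0.33 and 1.92 × 0.181 = 0.35 points. In the tabulated scenarios, one point of imbalance moves the risk difference by -0.04 to +0.07. At about 0.34 points, that is -1.4 to +2.4 percentage points. The latent-score model gives 1.2 to 2.5. The standard error of the difference is √[(0.735 × 0.265 + 0.45 × 0.55)/61] = 8.5 points, so the shift is at most about 2.5/8.5 = 0.29 standard errors.

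**5. Type I error.** The exact size of the crude test is 0.024 to 0.028 for common rates of 25% to 55%. Over the ten tabulated scenarios, simulated null rejection was 0.0225 to 0.0335 crude and 0.0210 to 0.0310 adjusted, with Monte Carlo standard error √(0.025 × 0.975/4000) = 0.0025. Conditional on a 1-SD imbalance favouring active, with slopes of 0.04 to 0.07 per point and a common rate of 45%, the crude size is about 0.039 to 0.049, against 0.028 unconditionally at that rate.

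**The case against.** The strongest reply is that nothing here is wrong. The hypotheses concern two marginal proportions, the planned test compares exactly those, and the sample size was computed for that test and reproduces. Randomization makes chance imbalance part of the sampling error the test already allows for. The endpoint is already scaled to each participant's own baseline, and an unadjusted test is simple to explain. The size of any gain comes from assumed inputs. A linear baseline term cannot follow the sawtooth, so the usable gradient comes mainly from assumed regression to the mean.

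All of this stands, and it limits the point. A reader might infer that the whole-point rule by itself costs precision. The documents do not support that: the rule gives no steady trend, regression to the mean can cancel its effect, and nothing supplied shows response by baseline. A reader might also take the conditional figures in step 5 to mean an inflated error rate. They describe one direction of imbalance; averaged over randomizations, the size is close to nominal.

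The objection does not show that adjustment is harmful. The worst case was about 1% more variance. Standardized estimates with a robust standard error do not need a correct working model for large-sample validity in a randomized trial, so the sawtooth limits the gain rather than the validity.

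**Conclusion.** The point holds as a modest improvement in efficiency and robustness, not as an error in the plan. The crude test leaves unused a covariate that is available before randomization and is part of the endpoint.

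Over the assumptions examined, adjustment changes the variance by between about +1% and -7% and power by about 0 to +2 points, with type I error essentially unchanged. A 1-SD baseline imbalance moves the observed difference by roughly 0 to 2.5 percentage points, against a planned difference of 28.5. These figures depend on an assumed baseline spread, assumed within-person variation and an assumed baseline-to-follow-up relation. If response is only weakly related to baseline, there is no gain.

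A reader might go further and call the primary result biased or the trial underpowered. Neither follows: randomization protects the crude comparison, and the 90% power stated in 2.6 is met without adjustment.

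**What to change.** In 2.5 and 2.7, pre-specify as the primary analysis a baseline-adjusted difference between the same two responder percentages:

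- Logistic regression of responder status on arm and baseline-visit rTNSS (continuous), standardized by g-computation to a marginal risk difference.
- A robust or influence-function standard error, tested at 1-sided 0.025, with a 95% CI.
- The crude Chi-square test retained as a sensitivity analysis.

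At the least, pre-specify the adjusted risk difference as a supporting analysis.

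Naming the baseline-visit score matters because rTNSS is also collected at screening. The endpoint, the hypotheses and N = 128 do not change. The cost is a few lines of text and some programming, with no new data, visits or participants. The downside is a slightly less simple primary analysis to explain, and possibly no gain.
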